2.10.4 Vital signs, weight and body mass index

Absolute change from baseline to highest and lowest post-baseline for systolic blood pressure, diastolic blood pressure, pulse rate and weight will be summarized by treatment group (EPO and EPO+DFX). A listing will be provided for systolic blood pressure, diastolic blood pressure, pulse rate weight and BMI. Notable systolic blood pressure, diastolic blood pressure, pulse rate and weight values will be flagged.

Note: Baseline is defined as the last available value prior to or on the day of first dose of study drug.

The criteria for notably vital signs and weight values is displayed in the table below.

The criteria for clinically notable abnormalities were defined as follows:

Clinically notable elevated values:

- Systolic BP: ≥ 160 mmHg or increase ≥ 20 mmHg from baseline
- Diastolic BP: ≥ 100 mmHg or increase ≥ 15 mmHg from baseline
- Weight: Increase from baseline of $\geq 7\%$
- Pulse: ≥ 100 bpm or increase from baseline of ≥ 15 bpm

Clinically notable below normal values:

- Systolic BP: ≤ 90 mmHg or decrease ≥ 20 mmHg from baseline
- Diastolic BP: ≤ 60 mmHg or decrease ≥ 15 mmHg from baseline
- Weight: decrease from baseline of $\geq 7\%$
- Pulse: ≤ 60 bpm or decrease from baseline of ≥ 15 bpm

2.10.5 Other safety data

Ocular and auditory examination will be collected at screening, nevertheless the examination(s) can be performed at any time if there is a need to be repeated. Data from these assessments will be flagged as appropriate and will be listed and summarized by treatment group. [REDACTED]

2.11 CSR Section 9.7.2: Sample size and power considerations

This is a pilot study that was planned to enroll approximately 60 patients considering site capabilities. No formal sample size calculation based on primary endpoint assumptions is performed.

However to give an idea regarding primary endpoint analysis, for a given number of 60 patients, under scenarios, where considering a minimal detectable differences of 20%, 30% and 40% assuming a reference response rate of 40% at 5% level of significance gives a 95% Agresti-Caffo confidence interval of (-0.04, 0.44), (0.068, 0.53) and (0.18, 0.62).

Clinical Development

ICL670

CICL670A2421

3.1 Randomization scheme and codes

Each patient will be identified in the study by a Patient Number, that will be assigned when the patient will be first enrolled for screening and will be retained as the primary identifier for the patient throughout his/her entire participation in the trial. The Patient Number consists of the [REDACTED], so that each patient will be numbered uniquely across the entire database.

Upon signing the informed consent form, the patient is assigned to the next sequential Patient Number.

The investigator or designated staff will contact the Interactive Web Response Technology (IWR) and provide the requested identifying information for the patient to register them into the IWR. Once assigned, the Patient Number must not be reused for any other patient and the Patient Number for that individual must not be changed, even if the patient is re-screened. If the patient fails to be randomized or start treatment for any reason, the reason will be entered into the Screening Log.

IWR must be notified within 2 days that the patient was not randomized.

3.2 Treatment assignment or randomization

Patients will be assigned to one of the 2 treatment arms in a ratio of 1:1.

The randomization numbers will be generated using the following procedure to ensure that treatment assignment is unbiased and concealed from patients and investigator staff. A patient randomization list will be produced by the IWR provider using a validated system that automates the random assignment of patient numbers to randomization numbers. These randomization numbers are linked to the different treatment arms, which in turn are linked to medication numbers. A separate medication randomization list will be produced by or under the responsibility of [REDACTED] using a validated system that automates the random assignment of medication numbers to medication packs containing each of the study treatments.

Prior to dosing, all patients who fulfill all inclusion/exclusion criteria will be randomized via IWR to one of the treatment arms. The investigator or his/her delegate will call or log on to the IWR and confirm that the patient fulfills all the inclusion/exclusion criteria.

3.3 Treatment blinding

This is an open-label study and the CTT is unblinded to the study treatment.

4 Clinical Study Report – Appendix 16.1.9 Documentation of statistical methods

This section of the RAP document presents further detail about the statistical methods not given in Section 9.7 of the Clinical Study Report (CSR).

4.1 Appendix 16.1.9 – Documentation of statistical methods

The statistical methods used to perform the analyses presented in the clinical study report will be described in Section 9.7. Section 16.1.9 will provide further details of the statistical methods not already provided in Section 9.7.

Clinical Development

ICL670

CICL670A2421

4.2 Definitions

4.2.1 Study drug and study treatment

Study treatments refers to EPO and EPO+DFX DT or EPO+DFX FCT.

Study drugs are DFX and EPO.

4.2.2 Date of first administration of study treatment

The date of first administration of study treatment will be derived as the first date when a non-zero dose of study treatment will be administered. For the sake of simplicity, the date of first administration of study treatment is referred to **start date of study treatment**. Start date of study treatment is defined by first non-zero dose administration date of EPO or EPO+DFX DT or EPO+DFX FCT.

The date of first administration for EPO and EPO+DFX DT or EPO+DFX FCT will be recorded on the corresponding “dosage administration record” (DAR) eCRF page.

4.2.3 Date of last administration of study drug

The date of last administration of study drug is defined as the last date when a non-zero dose of study treatment EPO or EPO+DFX DT or EPO+DFX FCT is administered and recorded on the DAR of the CRF. The date of last administration of study treatment is referred to **end date of study treatment or last date of study treatment**.

Note: For patients either randomized to EPO+DFX DT or EPO+DFX FCT or for patients who switch to EPO+DFX DT or EPO+DFX FCT after 12 weeks, the end date of study treatment could be the last date when a non-zero dose of DFX DT or DFX FCT is administered since EPO is administered weekly and the patient may have received the EPO 6 days before the last non-zero dose of DFX DT or DFX FCT is given.

4.2.4 Study start date

The start date of study should be considered to be the date when the first patient signs the informed consent form.

4.2.5 End of treatment

For a given patient the End of treatment will be defined as the **last day** when the patients received the study drug while still being on study.

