As the EPO guidelines only provide guidance for EPO use (EPO dosing, dose adjustments and dose discontinuation) and do not specify any criteria for the evaluation of erythroid response in MDS patients, in this study, the primary objective erythroid response will be assessed according to IWG criteria (Hb increase ≥ 1.5 g/dL) at 12 weeks of treatment. At any time, if Hb ≥ 12 g/dL, EPO will be stopped until the end of study. Patients treated with the combination therapy will stop EPO if Hb ≥ 12 g/dL and continue on DFX.

At 24 weeks, patients initially assigned to the combination therapy who showed Hb increase ≥ 1 g/dL at week 12 will be assessed for full hematological response according to IWG criteria (Erythroid response: Hb increase from baseline ≥ 1.5 g/dL; Neutrophil response: increase from baseline of $\geq 100\%$ and $> 0.5 \times 10^9/L$; Platelet response: increase from baseline of $\geq 30 \times 10^9/L$).

Patients initially treated with EPO alone and switched to the combination therapy with EPO and DFX after 12 weeks will be assessed for erythroid response at study end after 24 weeks of study treatment.

Figure 4-1 Study Design

Pre-treatment phase (Screening)

At Screening Visit (Visit 1) the investigator or his/her designee will assign a unique number to patients being considered for the study.

Prior to performing any study-related procedures or assessments, the patient must provide written consent to participation in this study. A screening period (up to 28 days) will be used to assess patient eligibility. Two Screening Visits will be required because key safety parameters need to be performed twice before the first dose administration ([Table 7-1](#)).

This study will use an Interactive Web Response (IWR) technology for randomization. Once the patient provides a signed informed consent form and eligibility is confirmed (all inclusion/exclusion criteria have been verified) the investigator and/or his designee can register the patient using the IWR.

Treatment phase

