2.10.3 Laboratory data

All laboratory values will be converted into SI units and the severity grade calculated using the low/normal/high classifications based on laboratory normal ranges and for selected parameters by notable and extended ranges as available in the deferasirox program standards.

Note that, Hemoglobin (g/dL) and Serum Ferritin (ng/mL) are the only exceptions which will be reported in US-units (if appropriate).

Table 2-4 Criteria for clinically notable and extended laboratory ranges

Parameter	Criteria
Absolute neutrophils	<1.5×10 ⁹ /L (extended range <0.5×10 ⁹ /L)
Platelets	<100×10 ⁹ /L (extended range <50×10 ⁹ /L)
ALT/AST	>5×ULN and >2×baseline value (extended range >10×ULN and >2×baseline value)
Serum creatinine	> 33% increase from baseline and >ULN at two consecutive measurements at least 7 days apart
Creatinine clearance	<60 mL/min at two consecutive measurements at least 7 days apart (extended range <40 mL/min)
Urinary total protein/creatinine ratio	>113.1 mg/mmol at two consecutive measurements at least 7 days apart

The frequency of laboratory abnormalities will be displayed by parameter and treatment group. Laboratory data will be summarized by presenting summary statistics of raw values at baseline and changes from baseline (absolute) to worst post-baseline value and by treatment group.

Laboratory data will be summarized by presenting **shift tables** showing baseline versus most extreme post-baseline result by notable range.

Box plots of absolute value will be provided for selected parameters.

Listings of all laboratory data with values flagged corresponding to normal/notable/extended ranges will be provided. The listing of all laboratory values will be provided by planned and actual dose along with the columns for treatment arm to which the patient was randomized and the treatment arm where the patient belongs at the time of the assessment will be provided.

Hematology:

Box plots on absolute value for Hb, neutrophil and platelets corresponding to each visit will be provided.

Absolute change from baseline to worst post-baseline value (the lowest for hematology parameters) will be provided for Hb, neutrophil and platelets.

Absolute change from baseline to last available value at the time of EOT will be provided for Hb, neutrophil and platelets.

Listings will be provided for Hb, platelets and neutrophils as well.

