Only listings will be provided for the parameters: Hematocrit, red blood cell (RBC) count, reticulocyte count, mean corpuscular volume (MCV), White blood cell (WBC) count with differential.

Blood chemistry

Absolute change from baseline to worst post-baseline value (the highest for blood chemistry parameters except creatinine clearance, which the lowest value is considered to be the worst) will be provided for serum ferritin, ALT, AST, total bilirubin, serum creatinine, creatinine clearance and urinary protein/creatinine ratio.

Absolute change from baseline to last available value at the time of EOT will be provided for serum ferritin, ALT, AST, total bilirubin, serum creatinine, creatinine clearance and urinary protein/creatinine ratio.

Shift tables from baseline to post-baseline value will be provided for serum ferritin, ALT, AST, serum creatinine, creatinine clearance and urinary protein/creatinine ratio in the following way:

Serum ferritin - Baseline categories: ≤ 270 ng/mL, $> 270 - 500$ ng/mL, $> 500 - 1650$ ng/mL, > 1650 ng/mL and Missing;

Serum ferritin - Post-baseline categories: ≤ 270 ng/mL, $> 270 - 500$ ng/mL, $> 500 - 1650$ ng/mL, > 1650 ng/mL.

ALT/AST - Baseline categories: \leq ULN, $> ULN - \leq 5 \times ULN$, $> 5 \times ULN - \leq 10 \times ULN$, $> 10 \times ULN$ and Missing;

ALT/AST - Post-baseline categories: \leq ULN, $> ULN - \leq 5 \times ULN$, One value $> 5 \times ULN$, One value $> 10 \times ULN$, Two consecutive values measured at least 7 days apart $> 5 \times ULN$, Two consecutive values measured at least 7 days apart $> 10 \times ULN$, $> 5 \times ULN$ and $2 \times$ Baseline value, $> 10 \times ULN$ and $2 \times$ Baseline value and Missing.

Serum creatinine - Baseline categories: \leq ULN, $>$ ULN and Missing;

Serum creatinine - Post-baseline categories: \leq ULN, One value $>$ ULN, Two values $>$ ULN, Two consecutive values measured at least 7 days apart $>$ ULN, Two consecutive values measured at least 7 days apart $>$ ULN, both $>$ 33% increase from baseline and Missing-

Urinary protein/creatinine ratio – Baseline categories: ≤ 22.62 mg/mmol, $>22.62 - \leq 113.1$ mg/mmol, > 113.1 mg/mmol and Missing; Post-baseline categories: ≤ 113.1 mg/mmol, One value > 113.1 mg/mmol, Two values > 113.1 mg/mmol, Two consecutive values measured at least 7 days apart > 113.1 mg/mmol and Missing.

Creatinine clearance - Classification I:

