4.2.11 Visit Windows

A year = 365.25 days.

A month = 365.25/12=30.4375 days.

Month 1 = Day (1;45] and then floor(n×30.4375) days±15 days, n=2, 3, 4,... that is Month 2 = Day (45;75]; Month 3 = Day (75;106]; etc.

For each parameter (i.e., hematologic and erythroid response), time windows will be used to identify data to be considered for the specific analysis at a specific time point. If there is more than one assessment within the time window, the last available assessment in that time window will be used. For all windows after baseline, only values after first dose of study drug will be used. Time windows are defined based on date of randomization (=study day 1; Visit 3 according to VES of protocol).

The following table shows the time windows for the analyses of responses based on planned assessment schedule.

Table 4-1 Visit windows

Planned assessment	Time window	Nominal day for visit
Baseline	Baseline; see definition 4.2.6	Baseline
Visit 3: Date of Randomization	Day 1	Day 1
Visit 4	Day 4 to Day 10*	Day 7
Visit 5	Day 11 to day 17*	Day 14
Visit 6	Day 18 to Day 24*	Day 21
Visit 7	Day 25 to Day 31*	Day 28
Visit 8	Day 35 to Day 49*	Day 42
Visit 9	Day 50 to Day 63*	Day 56
Visit 10	Day 77 to Day 91*	Day 84
Visit 11	Day 105 to Day 119*	Day 112
Visit 12	Day 133 to Day 147*	Day 140

The End of Treatment visit time window is Day 161 to Day 175 with nominal day of visit is Day 168 considering Visit 3 as Day 1.

In case of early treatment discontinuation or end of visit 12, the follow up will be 27-33 days from the last date when a non-zero dose of study treatment is administered (Last date of study treatment).

Considering, a patient has received EPO only and received a response. This patient will hold EPO until study end. However, Follow-up visit for them will be 30 days (+/- 3 days after EOT) and not 27-33 days from the last date when a non-zero dose of study treatment is administered.

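### The SAP gives EOT two incompatible meanings and does not say which one the change-to-EOT laboratory tables use; read literally, its definition takes held EPO-alone patients early

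*SAP*

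**What the plan says.** **The definition.** SAP 4.2.5 makes End of treatment the last day "when the patients received the study drug while still being on study". SAP 4.2.1 names the study drugs as DFX and EPO.

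**Where it is used.** SAP 2.10.3 states for hematology: "Absolute change from baseline to last available value at the time of EOT will be provided for Hb, neutrophil and platelets". For chemistry it states: "Absolute change from baseline to last available value at the time of EOT will be provided for serum ferritin, ALT, AST, total bilirubin", and the list goes on to creatinine, creatinine clearance and the urinary protein/creatinine ratio.

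**The other meaning.** SAP 4.2.11 states: "The End of Treatment visit time window is Day 161 to Day 175 with nominal day of visit is Day 168". SAP 2.6.1 ties EOT to CRF page 777, and protocol Table 7-1 labels Visit 777 as EOT. For an EPO-only responder, SAP 4.2.11 says "This patient will hold EPO until study end". It then counts that patient's follow-up visit from EOT and expressly not from the last non-zero dose.

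**The hold.** Under protocol 4.1, at any time that Hb is 12 g/dL or more, "EPO will be stopped until the end of study". Combination patients in that position stop EPO but continue DFX. SAP 4.2.3 notes that the last-dose date in patients on the combination may be that of DFX.

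**The concern.** An EPO-alone patient on hold has no other study drug but remains in the study. Under 4.2.5 this patient's EOT is the last injection before the hold. A combination patient with the same Hb course is still taking DFX, so EOT falls at the end of the study. Whether a patient has DFX is the randomized difference, so the shift in timing goes with the arm. It affects only patients whose Hb reaches 12 g/dL.

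The change-to-EOT tables would then set early values in part of the EPO column against week-24 values in the combination column. This matters most for creatinine, creatinine clearance, transaminases and proteinuria. SAP 2.10.3 specifies no by-visit change summary for these, so change to worst value, change to EOT and the shift tables carry the comparison.

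**Working it through.** **1. The plan's own figure.** Treatment lasts 24 weeks: 24 × 7 = Day 168. Adding and subtracting 7 days gives Day 161 to 175. This reproduces the EOT window in SAP 4.2.11, so there EOT is a visit.

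**2. The two meanings side by side.** If EOT were the last dose day, the contrast that SAP 4.2.11 draws for held patients, between counting from EOT and counting from the last non-zero dose, would be empty. The two sections cannot both hold for these patients.

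**3. Which Hb the 4.2.5 reading picks.** Inputs: nominal hematology days 1, 14, 28, 56, 84, 112 and 140 (SAP Table 4-1 with protocol 7.2.2.4.1), plus Day 42 if Visit 8 was done. EPO is weekly (protocol 6.1.1), assumed on Days 1, 8, 15 and so on. Rule: take the last Hb on or before the last EPO dose. Gap = 168 minus the day of that Hb. Two cases are shown, because central-laboratory results may come back after the next injection.

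| Hb ≥ 12 found at | No further dose: last dose → Hb used | Gap (days) | One more dose: last dose → Hb used | Gap (days) |
|---|---|---|---|---|
| Visit 5, Day 14 | Day 8 → Day 1 (baseline) | no post-baseline value | Day 15 → Day 14 | 154 |
| Visit 7, Day 28 | Day 22 → Day 14 | 154 | Day 29 → Day 28 | 140 |
| Visit 9, Day 56 | Day 50 → Day 28 (Day 42 if Visit 8 done) | 140 (126) | Day 57 → Day 56 | 112 |
| Visit 10, Day 84 | Day 78 → Day 56 | 112 | Day 85 → Day 84 | 84 |
| Visit 11, Day 112 | Day 106 → Day 84 | 84 | Day 113 → Day 112 | 56 |
| Visit 12, Day 140 | Day 134 → Day 112 | 56 | Day 141 → Day 140 | 28 |

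A trigger at Visit 8 (Day 42) gives Day 28 or Day 42. With no further dose, the Hb that triggered the hold is never the one used.

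**4. Other parameters.** Chemistry is also drawn at Visits 4 and 6. After a week-4 hold with last dose on Day 22, creatinine and transaminases are read at Visit 6, Day 21: 168 − 21 = 147 days early. Ferritin is drawn at Visit 3 and next at Visit 7, so the same patient has no scheduled post-baseline ferritin by Day 22.

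**5. The combination arm.** A patient who takes DFX to the end is read at about Day 168 under either meaning.

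**6. The Visit 777 reading.** Held EPO-alone patients and combination patients who stay to week 24 are both read at Day 161 to 175, so this asymmetry disappears. SAP 2.10.1, however, ends the on-treatment period 30 days after the last dose. A last dose on Day 22 gives 22 + 30 = Day 52; one on Day 78 gives 78 + 30 = Day 108. Day 168 lies outside both.

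**The case against.** A reader might infer that the SAP has chosen to compare EPO-alone values from weeks 2 to 8 with combination values from week 24. The documents do not support that, for three reasons.

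- **Likely intent.** Section 2.10.3 uses the abbreviation EOT, which 4.2.5 does not. Where the documents attach that abbreviation to something concrete, it is Visit 777. SAP 4.2.3 has a separate term for the last-dose date, and SAP 4.2.11 separates EOT from the last dose for exactly these patients. Visit 777 is probably meant.
- **Range.** Weeks 2 to 8 covers only holds at Visits 7 to 10 with no further dose. The hold can occur at any time, and one more injection is plausible.
- **Week 24.** This applies only to combination patients who stay on DFX to the end.

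The data are also not lost. SAP 2.9.2.4 and 2.9.2.5 summarise ferritin and Hb by visit, Hb, neutrophils and platelets have box plots at each visit, and all laboratory values are listed.

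All of this stands, and it limits the size of the point. It does not remove it: the only formal definition of End of treatment in the SAP is 4.2.5, and 2.10.3 does not point elsewhere. A programmer who follows the definitions section would produce the early values.

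**Conclusion.** The SAP carries two incompatible meanings of EOT, and 2.10.3 leaves open which one applies. This is an unresolved inconsistency, not a deliberately biased analysis. If 4.2.5 is followed, the Hb used for a held EPO-alone patient precedes Day 168 by 28 days at the least; in the extreme case there is no post-baseline value. At the two decision points in protocol Table 4-1 (weeks 4 and 12), with no further dose, the gap is 154 and 112 days.

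The reach is limited to the descriptive change-to-EOT safety tables. The primary endpoint counts any qualifying Hb rise within 12 weeks, and the secondary efficacy analyses do not use EOT.

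The day counts assume nominal visit days and weekly injections from Day 1. The Visit 777 reading assumes that held patients attend to week 24, as protocol 4.1 and SAP 4.2.11 imply. The documents give no hold rate, so the number of patients affected is unknown; each would be one of about 30 in the arm (60 randomized 1:1). SAP 1.1 defers table shells and derivations to Modules 7 and 8, which are not among these documents and might settle the meaning.

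**What to change.** 1. Reconcile SAP 4.2.5 with 4.2.11. For assessment tables, define EOT as the Visit 777 assessment. Keep the last-dose date in 4.2.3 for exposure.
2. In SAP 2.10.3, specify the last value available on or before the EOT visit (777).
3. In SAP 2.10.1, state that Visit 777 values of patients on an EPO hold enter these tables even when taken more than 30 days after the last dose, flagged as off drug. That section limits safety summaries to on-study assessments without distinguishing that term from the on-treatment period.

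**Cost.** A few SAP sentences and the matching programming. Protocol Table 7-1 already schedules the laboratory assessments at Visit 777.

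**Downside.** The tables will contain off-drug values for held EPO-alone patients. Timing will still differ for another group. Under protocol 4.1, combination patients with an Hb rise below 1 g/dL and Hb below 12 g/dL at week 12 leave the study, while EPO-alone patients with the same result switch and continue. A footnote giving the day of the EOT value by arm would show what difference remains.
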